10.1.5 Severity of pretreatment events and adverse events

The severity of adverse events shall be classified and defined as shown below.

Mild	The event is transient and easily tolerated by the subject.
Moderate	The event interrupts the subject's usual activities.
Severe	The event causes considerable interference with the subject's usual activities.

10.1.6 Causality of adverse events

The causal relationship of each PTE and adverse event to the study drug shall be classified and defined as shown below.

Related	An adverse event that follows a temporal sequence (including clinical course after discontinuation), or an adverse event in which there is at least a reasonable probability that a causal relationship to the study drug cannot be ruled out, although other factors such as underlying disease, concurrent diseases, or concomitant drugs/treatment are also suspected.
Not	An adverse event that does not follow a temporal sequence from administration of

related	the study drug. Very likely due to other factors such as underlying disease, concurrent diseases, or concomitant drugs/treatment.
---------	---

10.1.7 Relationship to study procedures

The relationship shall be recorded as “Yes” if the principal investigator or the investigator considers that there is reasonable possibility that an adverse event is due to a study procedure. Otherwise, the relationship shall be recorded as “No.”

10.1.8 Date of onset

The date of onset of adverse event shall be determined according to the following rules:

Adverse event, etc.	Date of onset
Signs, symptoms, diseases (diagnoses)	The date on which the first signs/symptoms were noted by the research subject and/or the principal investigator or investigator.
Asymptomatic diseases	The date on which a diagnosis was confirmed through a test(s). The date on which a diagnosis was confirmed, even when the test results indicate an old sign(s) of the disease or an approximate time of its onset.
Exacerbation of concurrent diseases or PTE	The date on which the first worsening of diseases/symptoms was noted by the research subject and/or the principal investigator or investigator.
Onset of a test abnormality after the start of the study drug administration (in case of PTE) (in case of AE)	The date on which a clinically significant laboratory abnormality was detected.
Worsening of a baseline test abnormality after initiation of study treatment	The date on which a clear increase/decrease in a laboratory parameter was clinically confirmed based on the time profile of the parameter.

10.1.9 Date of resolution

The date of resolution of an adverse event, etc. is the date on which the research subject recovered (including resolution with sequelae). If a research subject died due to the adverse event, etc. concerned, it shall be the date of death. The adverse event shall be recorded as “ongoing” if the research subject has not yet recovered by the end of the study.

10.1.10 Actions taken for the study drug

Actions taken for the study drug shall be classified or defined as shown below.

Drug withdrawn	
The study drug is discontinued because of an adverse event (including withdrawal by the research subject at his/her own discretion).
 
The case in which the study drug administration is continued after withdrawal from the study shall be categorized into “Dose not changed.”

Dose not changed	
The dose was not changed after the onset of the adverse event.
 
The study drug was discontinued, reduced, or increased because of another adverse event.
 
The study drug was discontinued or reduced for a reason other than the adverse event, e.g., inadvertence of the research subject.

Unknown	
It has not been possible to determine what action has been taken because the research subject is lost to follow-up.

Not Applicable	
The administration of the study drug had already been completed or discontinued before the onset of the adverse event.

10.1.11 Outcome

Outcome of adverse events is classified as follows:

Category	Criteria
Recovered	
Disappearance or recovery of symptoms and findings
 
Laboratory values returned to normal or baseline

Improved	
The intensity is lowered by one or more stages
 
Symptoms or findings mostly disappeared
 
Laboratory values improved, but have not returned to normal or baseline
 
The research subject died from a cause other than the concerned adverse event while the condition was resolving (recording of the date of death unnecessary)

Not recovered	
No change in symptoms, findings, or laboratory data
 
The symptoms, findings, or laboratory data on the final day of observable period were aggravated compared with the date of onset
 
Irreversible congenital anomaly
 
The research subject died from another cause before resolution of the concerned adverse event (recording of the date of death unnecessary)

Recovered with sequelae	
Disability that disturbs daily life

Death	
Direct relationship between death and the concerned adverse event
 
“Direct relationship” means that the concerned adverse event was the cause of death, or the concerned adverse event was clearly responsible for death.
 
Outcome of an adverse event which was not determined (judged, presumed) a direct cause of death observed in the same research subject is not considered as death.
 
The date of death shall be recorded.

Unknown	
Follow-up specified in the protocol after the date of onset was not possible due to

	change of hospitals or relocation, etc.
--	---

10.2 Procedures

10.2.1 Collection and reporting of adverse events

10.2.1.1 Adverse event collection period

The collection of PTEs shall start after the acquisition of informed consent and continue until the start of the study drug administration at Visit 2 (Day -15 to Day -1 before the start of study drug administration). If withdrawal was decided before the start of administration of the study drug, the collection of PTEs shall be terminated at that point.

Collection of the adverse events shall commence at the start of administration of the study drug to research subjects [at Visit 2 (Day -15 to Day -1 before the start of study drug administration)] and continue until completion of the treatment period [Visit 4 (Week 8)] or at discontinuation.

10.2.1.2 Reporting of adverse events

At each study visit, the principal investigator or investigator shall check for the presence of any onset of subjective symptoms. A neutral question, such as “How have you been feeling since your last visit?” may be asked to collect any adverse events that occurred between the previous and present visits.

When a PTE corresponds to a serious criterion, the principal investigator or investigator shall follow up all research subjects experiencing the PTE until the symptom resolve, any clinically significant abnormal laboratory values have returned to the baseline after acquisition of informed consent, or there is a satisfactory explanation for the change (permanent and irreversible PTEs). When the PTE does not correspond to a serious criterion, irrespective of the causal relationship with the procedure, follow-up of the research subject is not required by the protocol.

The principal investigator or investigator shall follow up all research subjects experiencing an adverse event irrespective of the causal relationship with the study drug, until the symptom resolve, or any clinically significant abnormal laboratory values have returned to baseline or there is a satisfactory explanation for the change (permanent and irreversible adverse events, etc.). All adverse events shall be recorded in the CRF. Name of adverse event, date of onset, date of resolution, grade, causal relationship with the study drug (i.e. "Unrelated" or "Related"), action taken for the study drug, outcome, relationship to study procedures, and severity shall be recorded.

Follow-up period of PTEs meeting any of the criteria for AEs and SAEs shall be until recovery of the adverse events, or the time when the principal investigator or investigator judges that further follow-up would be unnecessary.

10.2.2 Collection and reporting of serious adverse events

When a serious adverse event develops during the period of collecting adverse events, it shall be reported according to the following procedures. When a serious PTE develops, it shall also be reported in accordance with a procedure similar to that for serious adverse events.

At the time of onset of a serious adverse event or after notification of the onset by the research subject, the principal investigator shall report the serious adverse event to the head of the study site immediately, and the sponsor or CRO to whom the sponsor has entrusted responsibility shall notify the principal investigator of the study site.

The principal investigator shall then report the serious adverse event to the sponsor (for the contact information, refer to the attachment) within 1 working day of after notification of the onset. Further, the investigator shall submit a formal report within 10 calendar days to the sponsor.

Furthermore, it shall be mandatory to include the contents below in the report to be submitted to the sponsor within 1 working day, and other items shall be reported as far as possible.

- Brief description of adverse event and the reason for why it was determined as serious
- Research subject ID number
- Name of investigator or the subinvestigator
- Name of the study drug
- Determined causal relationship

10.2.3 Reporting of additional information concerning adverse events

If the sponsor requests provision of additional information concerning adverse events for reporting to regulatory authorities, the investigator or the subinvestigator shall confirm the necessary additional information and enter in the EDC system or submit a report within the period specified by the sponsor.

10.3 Follow-up of serious adverse events

When information that was not included in the detailed report was obtained later, the investigator or subinvestigator shall state it in the copy of the report on serious adverse events, or create another document and submit it to the contact address shown on the attached sheet. Relevant data collected

at the research implementing entity (e.g., ECG charts, laboratory test values, discharge summary, postmortem results) shall be sent to the sponsor or the committee such as the IEC upon request.

The investigator or the subinvestigator shall follow-up all serious adverse events, etc., until recovery is confirmed, or the final outcome is determined. In addition, serious PTEs shall also be followed, in accordance with procedure similar to that for serious adverse events.

10.3.1 Reporting of serious adverse events, etc., to Ethics Review Committee, etc., and regulatory authorities

When the head of study site receives a report of a serious adverse event from the principal investigator, the head of study site shall consult the Ethics Review Committee, etc., and notify the study sites that are conducting the clinical research through the sponsor or the CRO consigned by the sponsor.

When the principal investigator reported a serious adverse event for which a causal relationship to the research (study drug) cannot be ruled out and is unexpected, the head of the study site shall prepare a written report of the unexpected serious adverse event containing the information reported by the principal investigator plus the information below, and submit the report to the Minister of Health, Labour and Welfare, and notify other study sites conducting the clinical research. (The chief executive of the research implementing entity may report it to the Minister of Health, Labour and Welfare via the sponsor, and notify it to other clinical research implementing entities via the sponsor.) Serious PTEs shall also be reported in accordance with the same procedure as that for the serious adverse events. (No need to report to the Minister of Health, Labour and Welfare.)

- Actions taken for serious adverse events (discontinuation of new enrollment, revision of informed consent form, re-consents to other research subjects, etc.)
- Date of review, summary of review, result, necessary action, etc., related to Ethics Review Committee, etc.
- Notification to other research implementing entities

The sponsor shall report, in accordance with regulations, unexpected serious adverse drug reactions and other serious adverse events that are subject to emergency reporting to regulatory authorities, the investigators, and the head of study site.

From the time point of first acknowledging the event or receiving additional information, the sponsor or the CRO consigned by the sponsor shall comply with regulatory required time frames for reporting, and make emergency reports concerning unexpected serious adverse drug reactions and expected serious adverse drug reactions to regulatory authorities. Also, the sponsor shall, in the same way, make an emergency report of other critical safety information that may have a major effect on

the study drug risk-benefit, continuation of study drug administration, or continuation of clinical research. The research implementing entity shall submit copies of emergency report documents to the Ethics Review Committee, etc.

11.0 COMMITTEES ESTABLISHED FOR THIS STUDY

11.1 Clinical Endpoint Committee

The Central Assessment Committee members shall be independent specialists who have appropriate experience in the assessment of the parameters set as the endpoints of this research.

REGARDING THE PRIMARY ENDPOINT “%FMD (FASTING)” AND THE SECONDARY ENDPOINT “%FMD (4 H POSTPRANDIAL)”, THE CENTRAL ASSESSMENT COMMITTEE SHALL CONFIRM THE VALIDITY OF THE ASSESSMENT OF THE MEASUREMENT RESULTS ACCORDING TO THE PROCEDURE defined separately on the measured images reported from the FMD measuring study sites or measuring institutes.

The assessment results from the committee members shall be entered into the clinical research database and used for the analysis of endpoints.

12.0 DATA MANAGEMENT AND STORAGE OF RECORDS

Data management operations shall be performed according to the standard operating procedure by the data management department of the sponsor independent from the medical affairs department. Adverse events, PTE, medical history and concurrent disease shall be coded using the Medical Dictionary for Regulatory Activities (MedDRA). Drugs shall be coded using the WHO (World Health Organization) Drug Dictionary.

12.1 Case report form

The principal investigator or investigator shall complete a CRF for each research subject who has signed the informed consent form.

The sponsor or the designee shall provide access rights to the electric CRF system to the study site. Before use of the electric CRF system, the sponsor shall provide training to the principal investigator, investigators, and study collaborators. The CRF shall be used to report the information collected during the study period to the sponsor. CRF must be completed in Japanese. Data shall be directly entered in preparing the CRF.

A change or correction of the CRF shall be recorded as an audit trail that records the information before and after the change or correction, the person who made the change or correction, date of change or correction, and its reason.

The investigator the designee shall ensure the accuracy and completeness of the CRF, and provide an electronic signature on the relevant page of the case report form. The principal investigator shall bear full responsibility for the accuracy and reliability of all data entered on the CRF.

The following data shall be recorded on the CRF directly (except for the data included in the source documents).

- Eligibility, completion status, reason for discontinuation, the seriousness, severity, relation to study drug and study procedures outcome

The following data shall not be recorded directly into the CRFs.

- Laboratory test values
- FMD/Vessel caliber measurement results
- Measurement results from panels of blood proteins, unsaturated fatty acid metabolites, and lipids

When the principal investigator or the investigator makes a change or correction in the data entered on the CRF after fixation of clinical data base, a record (Data Clarification Form) of change or correction on the CRF provided by the sponsor shall be used. The principal investigator shall

confirm that the record of change or correction on the CRF is accurate and complete, and sign or write name/affix a seal, and date it.

The sponsor or the designee shall confirm that the CRFs are completed appropriately according to the procedures set by research. The sponsor or the designee shall have access to the medical records of the research subjects and in-house records to ensure the accuracy of the CRF as necessary. The completed CRF is the property of the sponsor, and the principal investigator or investigator shall not disclose the information to a third party without a written permission from the sponsor.

12.2 Timing of data entry into the electronic CRF system

The sponsor or the designee shall request the principal investigator and investigator to promptly enter data into the EDC following enrolment of the research subject, each visit during study treatment, completion/discontinuation of the study, and follow-up period.

12.3 Storage of records

The principal investigator or the chief executive of the study site shall store the following materials, including those specified in Section 12.1, and study-specific documents to be investigated or audited by the regulatory authority and the sponsor or the designee. The documents include research subject ID code, medical records, clinical study worksheets (if used), original signed and dated informed consent forms, the record of change or correction on the CRF (copy), and electric copies of electronic CRF including audit trail. The principal investigator and the chief executive of the study site shall appropriately retain the material/information related to this study for at least 5 years from the date of reporting the end of the research by the principal investigator, or for 3 years from the date of reporting final publication of the study result, whichever date is later. However, when the sponsor requires a longer storage period, the chief executive of the study site shall discuss the period and methods of storage with the sponsor.

13.0 STATISTICAL ANALYSIS METHODS

The person in charge of analysis and the designee [analysis personnel, who belongs to contract research organization (CRO) independent from the sponsor] shall perform the statistical analysis. The sponsor will not be involved in the statistical analysis.

13.1 Statistical and analytical plans

The analysis personnel shall prepare a statistical analysis plan before the acquisition of the informed consent of the earliest research subject, and issue the first edition. Detailed definition of endpoints and analytical methods should be specified in the SAP to deal with all the purposes of the research.

13.1.1 Analysis set

Two analysis sets, “Full Analysis Set ; FAS” and “Safety Analysis Set ; SAS” are used in this research. The FAS primarily used for efficacy analysis will be defined as “research subjects who have been randomized and received the study drug at least once”, and the SAS as “research subjects who have received the study drug at least once during the clinical research”.

13.1.2 Analysis of demographic and other baseline characteristics

From “SAS” primary research subject background items will be tabulated.

13.1.3 Efficacy analysis

From FAS the following shall be analyzed.

13.1.3.1 Analysis of primary endpoints

%FMD(fasting)

[Analytical method]

- 1) Summary statistics by treatment group (number of subjects, mean, SD, minimum value, maximum value, quartiles) and a two-sided 95% confidence interval for the mean will be calculated at each evaluation time point during the treatment period, and a diagram illustrating the change in the mean \pm SD will be prepared.
- 2) The change for each treatment group (Treatment Period Visit 3 or Visit 4 - Treatment Period Visit 2) will be calculated at each evaluation time point during the treatment period and the same analysis as in 1) will be performed.
- 3) Using fasting TG at the start of treatment, a stratified analysis on summary statistics by treatment group (number of subjects, mean, SD, minimum value, maximum value, quartiles) and a two-sided 95% confidence interval for the mean will be performed.

13.1.3.2 Analysis of secondary endpoints

- ① %FMD (4 h postprandial)
- ② TG level (fasting)
- ③ TG level (4 h postprandial)
- ④ Plasma fatty acid fraction

[Analytical method]

- 1) Summary statistics by treatment group (number of subjects, mean, SD, minimum value, maximum value, quartiles) and a two-sided 95% confidence interval for the mean will be calculated at each evaluation time point during the treatment period, and a diagram illustrating the change in the mean \pm SD will be prepared.
- 2) The change for each treatment group (Treatment Period Visit 3 or Visit 4 - Treatment Period Visit 2) will be calculated at each evaluation time point during the treatment period and the same analysis as in 1) will be performed.
- 3) Using fasting TG at the start of treatment, a stratified analysis on summary statistics by treatment group (number of subjects, mean, SD, minimum value, maximum value, quartiles) and a two-sided 95% confidence interval for the mean will be performed.

13.1.3.3 Analysis of other endpoints

Efficacy endpoints:

Total cholesterol, LDL-C, LDL-C, Remnant-like particle (RLP) cholesterol , Apoprotein B-48, C-reactive protein (CRP), 8-epi-PGF2 α quantitative (urinary)

Analytical method

- 1) Summary statistics by treatment group (number of subjects, mean, SD, minimum value, maximum value, quartiles) and a two-sided 95% confidence interval for the mean will be calculated at each evaluation time point during the treatment period, and a diagram illustrating the change in the mean \pm SD will be prepared.
- 2) The change for each treatment group (Treatment Period Visit 3 or Visit 4 - Treatment Period Visit 2) will be calculated at each evaluation time point during the treatment period and the same analysis as in 1) will be performed.

Exploratory endpoints:

Exploratory biomarker evaluation

(1) Panel of blood proteins

PAI1, TFPI, TNF- α , IL-1, IL-6, IL-8, IL-10, INF γ , MCP-1, ICAM1, VCAM1, eSelectin, serum amyloid A (SAA), pentraxin 3 (PTX3), FABP4, leptin, adiponectin

(2) Panel of unsaturated fatty acid metabolites

EPA metabolites (18-HEPE, 5-HEPE, Resolvin E1), DHA metabolites [17-HDHA (17-HDoHE), 7-HDHA (7-HDoHE), Resolvin D1, Resolvin D2, Resolvin D3, Maresin 1], and Arachidonic acid metabolites (PGE2, PGD2, PGF2 α , TXB2, 6-keto-PGF1 α , LTB4)

Analytical method

1. Summary statistics by treatment group (number of subjects, mean, SD, minimum value, maximum value, quartiles) and a two-sided 95% confidence interval for the mean will be calculated at each evaluation time point during the observation and treatment period, and a diagram illustrating the change in the mean \pm SD will be prepared.
2. The change for each treatment group (Treatment Period Visit 2, Visit 3 or Visit 4 - Treatment Period Visit 1) will be calculated at each evaluation time point during the observation and treatment period and the same analysis as in 1) will be performed.
3. The change for each treatment group (Treatment Period Visit 3 or Visit 4 - Treatment Period Visit 2) will be calculated at each evaluation time point during the treatment period and the same analysis as in 1) will be performed. Moreover, the correlation coefficient will be calculated with the change of % FMD for each treatment group and drawn a scatter plot.

(3) Panel of lipids (fasting)

Phospholipids (glycerophospholipid (phosphatidylcholine, phosphatidylethanolamine, phosphatidylglycerol, phosphatidylserine, etc.), sphingophospholipids (sphingomyelin, etc.)), sphingolipid (ceramide, ganglioside, sulfatides, etc.), neutral lipids (monoacylglycerol, diacylglycerol, triacylglycerol, cholesteryl esters, dolichol, etc.), fatty acids (free fatty acids), acylcarnitine, bile acids, ubiquinone, and molecular species related to these biosynthesis and metabolism

Analytical method

1. Summary statistics by treatment group (number of subjects, mean, SD, minimum value, maximum value, quartiles) and a two-sided 95% confidence interval for the mean will be calculated at each evaluation time point during the observation and treatment period, and a diagram illustrating the change in the mean \pm SD will be prepared.
2. The change for each treatment group (Treatment Period Visit 2, Visit 3 or Visit 4 - Treatment Period Visit 1) will be calculated at each evaluation time point during the observation and treatment period and the same analysis as in 1) will be performed.
3. The change for each treatment group (Treatment Period Visit 3 or Visit 4 - Treatment Period Visit 2) will be calculated at each evaluation time point during the treatment period and the same analysis as in 1) will be performed. Moreover, the correlation coefficient will be calculated with the change of % FMD for each treatment group, and scatter plots will be drawn.

(4) Panel of lipids (4 h postprandial)

Phospholipids (glycerophospholipid (phosphatidylcholine, phosphatidylethanolamine, phosphatidylglycerol, phosphatidylserine, etc.), sphingophospholipids (sphingomyelin, etc.)), sphingolipid (ceramide, ganglioside, sulfatides, etc.), neutral lipids (monoacylglycerol, diacylglycerol, triacylglycerol, cholesteryl esters, dolichol, etc.), fatty acids (free fatty acids), acylcarnitine, bile acids, ubiquinone, and molecular species related to these biosynthesis and metabolism

Analytical method

1. Summary statistics by treatment group (number of subjects, mean, SD, minimum value, maximum value, quartiles) and a two-sided 95% confidence interval for the mean will be calculated at each evaluation time point during the observation and treatment period, and a diagram illustrating the change in the mean \pm SD will be prepared.
2. The change for each treatment group (Treatment Period Visit 3 or Visit 4 - Treatment Period Visit 2) will be calculated at each evaluation time point during the treatment period and the same analysis as in 1) will be performed. Moreover, the correlation coefficient will be calculated with the change of % FMD for each treatment group, and scatter plots will be drawn.

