Much remains unknown in terms of the changes in endothelial cell-derived cytokines which are well known to correlate with progression of arteriosclerosis, as well as the activities of inflammatory cells as a chronic inflammation lesion in a cytokine assay panel. In addition, an unfinished work is to elucidate an additional mechanism of action by analyzing the in vivo changes in the whole lipids after treatment with Lotriga[®] (EPA/DHA preparations). Thus, blood proteins and lipids/unsaturated fatty acid metabolites which are associated with blood vessel inflammation will be measured to search for potential biomarkers which may correlate with the change in FMD, and to explore the mechanism of TG-lowering and antiatherosclerotic activities by the combination of HMG-CoA reductase inhibitor and Lotriga[®] (EPA/DHA preparations).

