13.3 Determination of the number of planned research subject

40 patients evaluable for the primary endpoint

(Omega-3-acid ethyl esters 2 g: 20 patients, Omega-3-acid ethyl esters 4 g: 20 patients)

Exploratory biomarkers will be measured only for the research subjects from whom blood is taken during the observation period after approval of the revised protocol (the 2nd edition) by the committee such as the IEC.

[Rationale for the number of planned research subjects]

The planned sample size is based on the feasibility to explore the effects of omega-3-acid ethyl esters on vascular endothelial function.

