10.5. Multiple Comparisons/Multiplicity

It does not adjust multiplicity.

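### Biomarker–%FMD correlations are planned only within each arm and without confidence intervals, and the 4-h lipid panel has no matching %FMD at Visit 3

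*Protocol*

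**What the plan says.** Protocol 4.1 gives the purpose of the biomarker work: to "search for potential biomarkers which may correlate with the change in FMD", and to explore mechanism.

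Protocol 13.1.3.3 serves the first aim with one instruction. For the protein and metabolite panels it reads: "Moreover, the correlation coefficient will be calculated with the change of % FMD for each treatment group and drawn a scatter plot". For the fasting and 4-h lipid panels the wording is nearly the same: "the correlation coefficient will be calculated with the change of % FMD for each treatment group, and scatter plots will be drawn". In each case the changes are Visit 3 minus Visit 2 and Visit 4 minus Visit 2. The section does not give the type of coefficient, a confidence interval for it, an estimate across both arms, or a rule for calling a marker a candidate. It also does not say whether fasting or 4-h %FMD is meant.

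Protocol 13.3 sets the size at "40 patients evaluable for the primary endpoint" ("Omega-3-acid ethyl esters 2 g: 20 patients, Omega-3-acid ethyl esters 4 g: 20 patients"), on grounds of feasibility. It adds a restriction: "Exploratory biomarkers will be measured only for the research subjects from whom blood is taken during the observation period after approval of the revised protocol" (second edition). The size of that subset is not stated.

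SAP 10.5 says "It does not adjust multiplicity". According to the SAP revision history, however, the biomarker section was removed at version 3.0 and the analysis put off until after March 2018. Protocol 13.1.3.3 is therefore the only biomarker plan in these documents.

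**The concern.** Whether a marker moves with FMD is, on the stated aim, one question for the study. Answering it only arm by arm halves the sample behind each coefficient. It leaves two imprecise answers per analyte and visit, with no stated way to read them together. Without intervals, a reader of a long list of coefficients has little to go on except size, and at about 20 patients the largest values can be large by chance alone.

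The second issue is one of timing. The 4-h lipid panel is to be correlated with the change in %FMD at Visit 3, but 4-h %FMD is not scheduled at that visit.

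At stake is which markers are carried forward as candidates. No primary, secondary or safety result is affected.

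**Working it through.** The plan states no power, correlation or detectable effect for this analysis, so there is no figure of its own to reproduce.

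**Inputs**
- Analytes named in 13.1.3.3: 17 proteins + 15 metabolites (3 EPA, 6 DHA, 6 arachidonic acid) = 32. The two lipid panels are open-ended, so 32 is a floor.
- Arms: 2. Change time points: 2.
- n: 20 per arm, 40 in total (13.3). As an assumption for a smaller subset: 15 per arm, 30 in total.
- Two-sided 5%: assumed, in line with the SAP's 95% two-sided estimation. The plan names no test.

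**Number of coefficients**

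32 × 2 arms × 2 visits = 128, before any lipid species.

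**Chance values**

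- Critical |r| = t/√(t² + df). At n=20, df=18 and t=2.101, so |r| = 0.444.
- Expected number beyond it if nothing is correlated: 128 × 0.05 = 6.4. Dependence between analytes does not change this expectation.
- For 32 independent null analytes in one arm at one visit, the median of the largest |r| solves P(|r| < c)^32 = 0.5, giving c ≈ 0.51.

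**Precision and power at r=0.4**

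Fisher z: atanh(0.4) = 0.4236. The standard error is 1/√(n−3) within an arm and 1/√(n−4) for a partial correlation adjusted for arm. Power is Φ(0.4236/SE − 1.96).

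| Analysis | SE | 95% CI if r=0.4 is observed | Power if true r=0.4 |
|---|---|---|---|
| One arm, n=20 | 1/√17 = 0.243 | -0.05 to 0.72 | 42% |
| One arm, n=15 | 1/√12 = 0.289 | -0.14 to 0.76 | 31% |
| Both arms, adjusted, n=40 | 1/√36 = 0.167 | 0.10 to 0.64 | 72% |
| Both arms, adjusted, n=30 | 1/√26 = 0.196 | 0.04 to 0.67 | 58% |

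Within one arm of 20, power is 25% at a true r of 0.3, 62% at 0.5 and 82% at 0.6. These are unadjusted figures for a Pearson-type coefficient under bivariate normality.

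**Share of chance findings**

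If a proportion π of analytes is truly correlated and each is screened at 5%, the false share is 0.05(1−π) / [0.05(1−π) + π × power]. At n=20:
- π=5%, r=0.3: 0.0475 / (0.0475 + 0.05 × 0.247) = 79%.
- π=30%, r=0.6: 0.035 / (0.035 + 0.30 × 0.815) = 13%.

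The documents give neither π nor a screening threshold.

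**Visit 3 pairing**
- Protocol 13.1.3.3, 4-h lipid panel: correlation planned for Visit 3 and Visit 4 changes.
- Protocol 9.3.3 (Visit 3): 4-h biomarker sampling is listed, but the FMD test is fasting only.
- Appendix A: 4-h FMD at Visit 2, Visit 4 and discontinuation, not at Visit 3.
- SAP 7.2: week 4 is excluded for 4-h %FMD.

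At Visit 3, then, a fed-state lipid change could be paired only with fasting %FMD. At Visit 4 both are measured and the text does not say which applies.

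**The case against.** The strongest reply is that this is an exploratory tier. The plan asks for coefficients and plots, sets no test or cut-off, and describes every efficacy endpoint by arm. Unadjusted description in such a tier is not an error. That stands, and no multiplicity procedure is required here.

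A reader might infer that the search will mostly return chance hits and miss real ones. The documents do not support that. The false share runs from about 13% to 79% over the assumptions shown above. A true correlation of 0.6 or more would usually be detected even in one arm of 20.

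Nor does SAP 10.5 prove that the biomarker analysis lacks multiplicity control. It stands in a SAP from which that analysis was removed, and any later biomarker plan is not among the documents.

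The gain from 42% to 72% is an unadjusted one. In a simulation with Benjamini-Hochberg flagging at 10%, arm adjustment at n=40, 17 independent analytes and true r=0.4, power was about 43% with one true analyte and 62% with six. False discovery rate flagging would therefore give back much of the gain when true markers are few.

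Pooling also assumes a similar within-arm relation at 2 g and 4 g, which the documents do not establish. Per-arm plots are useful for checking that and should stay. Finally, 20 per arm is a target rather than a cap, and how far the second-edition rule reduces it is unknown.

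These points leave two gaps: no interval or combined estimate for the question the biomarker work was added to answer, and an unmatched pairing at Visit 3. On the latter, a coefficient with fasting %FMD remains computable, but the plan does not say that this is what it intends.

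**Conclusion.** The concern holds as a matter of efficiency and clarity, not as an error that invalidates a result. The per-arm coefficients are imprecise for moderate correlations. Using both arms with adjustment for dose narrows the interval at r=0.4 from a width of 0.77 (-0.05 to 0.72) to 0.54 (0.10 to 0.64), with data already to be collected. About 6 of the 128 coefficients for named analytes would pass |r|=0.44 if none were real, and the open-ended lipid panels add to that by an amount the documents do not let one count.

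The figures rest on 20 evaluable patients per arm with biomarkers, a two-sided 5% level that the plan does not state, approximate bivariate normality and, for the combined estimate, a common within-arm correlation. With fewer biomarker patients both analyses are less precise.

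The Visit 3 mismatch rests on none of these assumptions. It follows directly from the schedule.

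**What to change.** In Protocol 13.1.3.3, and in whatever plan governs the deferred biomarker analysis:

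1. Add, as the lead summary, one partial (preferably rank) correlation per analyte across both arms, adjusted for arm, on the Visit 4 minus Visit 2 change, with a 95% CI.
2. Keep the per-arm coefficients and scatter plots as supportive, to show whether the relation differs by dose.
3. State the pairing: fasting panels with fasting %FMD, the 4-h lipid panel with 4-h %FMD. Drop the Visit 3 correlation for the 4-h panel.
4. Report how many coefficients were examined. False discovery rate flagging is optional; for an exploratory analysis the count and the intervals are enough.

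The cost is wording and minor programming, with no new samples or visits. The downside is that the combined estimate could mislead if the relation differs between 2 g and 4 g, which the retained per-arm results let readers check, though only roughly at this size.
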